## **PRÉCIS**

### **Background:**

- Tumor-induced osteomalacia (TIO) is a rare disorder in which fibroblast growth factor (FGF23)-producing neoplasms cause renal phosphate wasting and skeletal disease.
- Recent studies have shown that chromosomal translocations causing a fibronectin-FGFR1 (FN1/FGFR1) fusion gene have been identified in 40-60% of these tumors.
- BGJ398 is an orally bio-available, selective and ATP competitive pan-fibroblast growth factor receptor (FGFR) kinase inhibitor which has demonstrated anti-tumor activity in preclinical, in vitro and in-vivo tumor models harboring FGFR genetic alterations.

### **Objectives:**

To induce complete metabolic response in subjects with tumor-induced osteomalacia (TIO) with BGJ-398 as demonstrated by normalization of FGF23 and phosphate homeostasis.

### **Eligibility:**

Patients may be eligible if they:

- Are adults 18-85 years with documented evidence of TIO due to a non-localized or unresectable tumor, or metastatic disease, or resectable tumor that cannot be easily removed.
- Are not taking any exclusionary medications or foods that may interfere with BGJ398.
- Are not pregnant or nursing and are willing to use contraception (at least two forms of contraception), if able to become pregnant.
- Have no significant ophthalmologic, gastrointestinal, renal, or hematologic disease.

### **Design:**

- Phase 2, open-label, non-randomized, single-arm, drug treatment trial.
- 10 subjects to be studied.
- Treatment duration 6 months with 3 months off drug follow-up and optional extension phase.
- Monthly NIH visits with additional labs obtained in between visits.
- Imaging performed in those with identifiable tumors.
- Analyses to include repeated measures ANOVA assessing changes in biochemical indices over time in response to BGJ398.

### **List of Abbreviations**

AE	Adverse Event
ALT	Alanine aminotransferase
ANC	Absolute Neutrophil Count
ANOVA	Analysis of variance
ANCOVA	Analysis of covariance
AST	Aspartate aminotransferase
BMD	Bone mineral density
CBC	Complete Blood Count
CRF	Case Report Form
CT	Computed Tomography
CYP	Cytochrome p450 isoenzyme
DCC	Data Coordinating Center
DNA	Deoxyribonucleic Acid
DSMC	Data and Safety Monitoring Committee
eCRF	Electronic Case Report Form
eGFR	Estimated Glomerular Filtration Rate
FDA	Food and Drug Administration
FDG-PET/CT	fluorodeoxyglucose-positron emission tomography/CT
FGF23	Fibroblast Growth Factor-23
FGFR1	Fibroblast Growth Factor Receptor-1
IND	Investigational New Drug Application
IRB	Institutional Review Board
ITT	Intent-to treat
MCV	Mean Corpuscular Volume
NIDCR	National Institute of Dental and Craniofacial Research
BGJ398	Tyrosine kinase inhibitor-investigational drug.
NIH	National Institutes of Health
PRPL	Patient Recruitment and Public Liaison
QoL	Quality of Life
RDW	Red Cell Distribution Width
RSC	Radiation Safety Committee

*Abbreviated Title: BGJ398 in TIO*  
*Version Date: 21MAY2019*

SAE	Serious Adverse Event
TIO	Tumor Induced Osteomalacia
TmP/GFR	Tubular maximum reabsorption of phosphate/GFR
TRP	Tubular reabsorption of phosphate
UP	Unanticipated Problem
ULN	Upper Limit Normal
WBC	White Blood Cells

## 1. INTRODUCTION

### 1.1 STUDY OBJECTIVES

#### 1.1.1 Primary Objective:

- To induce complete metabolic response in subjects with tumor-induced osteomalacia (TIO) with BGJ398 as demonstrated by normalization of FGF23 and phosphate homeostasis.

#### 1.1.2 Secondary Objective:

- To evaluate the effects of BGJ398 on:
  - o mineral homeostasis
  - o quality of life
  - o muscle strength.
- To evaluate the effects of BGJ-398 on radiographic evidence of TIO.

**Table 1** summarizes the primary, secondary and exploratory objectives tagged with the associated endpoints and evaluation criteria:

	Objective	Endpoint Measures
Primary	Complete metabolic response	Normalization of blood phosphate and FGF23 off study drug
Secondary/Exploratory	Pharmacodynamics of mineral homeostasis response to BGJ398 in TIO	Changes in FGF23 (intact and C-terminal), Phosphorous, 1, 25 (OH) 2 vitamin D; TRP, TmP/GFR
	Effects on quality of life	Standardized measures of QoL
	Effects on muscle strength	Standardized muscle strength testing
	Effect on radiographic evidence of TIO	Changes in clinically-indicated FDG-PET/CT, octreotide SPECT/CT, or  Ga-DOTATATE PET/CT scan
	Assess safety/tolerability	Percentage of patients who incurred grade 3 or 4 adverse events (AEs) or serious adverse events (SAE) or AEs causing dose interruption/reduction

### 1.2 BACKGROUND AND RATIONALE

Tumor-induced osteomalacia (TIO) is a rare neoplastic syndrome that is associated with fractures, bone pain, and muscle weakness (*1*). The vast majority of cases are caused by fibroblast growth

*Abbreviated Title: BGJ398 in TIO*

*Version Date: 21MAY2019*

factor-23 (FGF23)-secreting mixed connective tissue mesenchymal tumors. FGF23 acts by binding to target cells via an FGF receptor (FGFR1), but signaling requires the co-receptor Klotho (2). Activation of FGFR1 leads to inhibition of sodium-phosphate co-transporters in the proximal tubule cells, resulting in decreased tubular phosphate reabsorption, increased renal phosphate excretion, and hypophosphatemia (3). In addition, FGF23 downregulates  $1\alpha$ -hydroxylase and up-regulates 24-hydroxylase, resulting in decreased production of the active form of vitamin D, 1, 25-dihydroxy vitamin D, further contributing to hypophosphatemia. While tumor resection can cure TIO, tumors are typically small (often < 2 cm) and notoriously difficult to locate. Medical treatment of patients whose tumors cannot be located, or are inoperable or widely metastatic, is difficult. It involves at least thrice daily phosphate, which is poorly tolerated due to diarrhea, and active vitamin D. Frequent monitoring with careful adjustment of medications is required to prevent untoward effects of medical therapy, including secondary/tertiary hyperparathyroidism hypercalcemia, hypercalciuria, nephrocalcinosis, and nephrolithiasis.

Recently, translocations resulting in a fibronectin-fibroblast growth factor receptor-1 (FN1/FGFR1) fusion gene were identified in 40-60% of the tumors investigated, suggesting a driver role for FGFR1 signaling in TIO tumorigenesis (4, 5). Thus, it was hypothesized that an FGFR inhibitor may be effective therapy and possibly tumoricidal in TIO.

## **2 ELIGIBILITY ASSESSMENT AND ENROLLMENT**

### **2.1 ELIGIBILITY CRITERIA**

#### **2.1.1 Inclusion Criteria**

Patients eligible for inclusion in this study have to meet **all** of the following criteria:

1. Aged 18-85 years

*Abbreviated Title: BGJ398 in TIO*

*Version Date: 21MAY2019*

2. Diagnosis of TIO due to a non-localized or unresectable tumor, or metastatic disease or resectable tumor that cannot be removed by minor surgical procedure. This diagnosis will be confirmed prior to enrollment on protocol 01-D-0184. Where clinically indicated, genetic testing to rule-out heritable causes of FGF23 excess will also be performed on 01-D-0184.
3. Willing and able to comply with scheduled visits, treatment plan and laboratory tests.
4. Able to swallow and retain oral medication.
5. Able to provide informed consent

### **2.1.2 Exclusion criteria**

Patients eligible for this study must not meet **any** of the following criteria:

1. Have another genetic or secondary cause of hypophosphatemia.
2. History of any other malignancy that has not been cured/in remission for 5 years.
3. Patients who previously received treatment with an FGFR inhibitor other than BGJ398.
4. Current evidence of corneal or retinal disorder/keratopathy including, but not limited to: bullous/band keratopathy, corneal abrasion, inflammation/ulceration, keratoconjunctivitis, confirmed by ophthalmologic examination
5. Impairment of gastrointestinal (GI) function or GI disease that may significantly alter the absorption of oral BGJ398 (e.g., ulcerative diseases, uncontrolled nausea, vomiting, diarrhea, malabsorption syndrome, small bowel resection)
6. Patients who are currently receiving treatment with agents that are known strong inducers or inhibitors of CYP3A4 are prohibited. This includes treatment with enzyme-inducing antiepileptic drugs including carbamazepine, phenytoin, phenobarbital, and primidone.
7. Consumption of grapefruit, grapefruit juice, pomegranates, star fruits, Seville oranges or products within 7 days prior to first dose
8. Use of amiodarone within 90 days prior to first dose
9. Current use of therapeutic doses of warfarin sodium or any other coumadin-derivative anticoagulants. Heparin and/or low molecular weight heparins are allowed.
10. Insufficient bone marrow function defined as all of the following:
  - ANC <1,500/mm^3 [1.0 x 10^9/L] AND
  - Platelets < 75,000/mm^3 [75 x 10^9/L] AND
  - Hemoglobin < 10.0 g/dL
11. Insufficient hepatic and renal function defined as one of the following:
  - Total bilirubin > 1.5x ULN OR
  - AST/SGOT and ALT/SGPT > 2x ULN OR
  - Blood creatinine > 1.5xULN and/or calculated eGFR < 45 ml/min/1.73 m^2 (calculated by CKD-Epi)
12. Clinically significant cardiac disease including any of the following:
  - Congestive heart failure requiring treatment (NY Heart Association grade ≥ 2),
  - History or presence of clinically significant ventricular arrhythmias, atrial fibrillation, resting bradycardia, or conduction abnormality

*Abbreviated Title: BGJ398 in TIO*

*Version Date: 21MAY2019*

- Unstable angina pectoris or acute myocardial infarction  $\leq$  3 months prior to starting study drug
  - QTcF > 450 msec (males); > 470 msec (females)
  - History of congenital long QT syndrome
13. Recent ( $\leq$ 3 months) transient ischemic attack or stroke
14. Patients under age 21 will have a bone age assessed as part of their clinically indicated skeletal survey under 01-D-0184 and will not be offered enrollment if their growth plates are open.
15. Pregnant or nursing (lactating) women, where pregnancy is defined as the state of a female after conception and until the termination of gestation, confirmed by a positive hCG laboratory test
16. Women of child-bearing potential, defined as all women physiologically capable of becoming pregnant, unless they are using highly effective methods of contraception during dosing and for 3 months following the discontinuation of study treatment. Highly effective contraception methods include:
- Total abstinence (when this is in line with the preferred and usual lifestyle of the subject. Periodic abstinence (e.g., calendar, ovulation, symptothermal, post-ovulation methods) and withdrawal are not acceptable methods of contraception
  - Female sterilization (have had surgical bilateral oophorectomy with or without hysterectomy) or tubal ligation at least six weeks before taking study treatment. In case of oophorectomy alone, only when the reproductive status of the woman has been confirmed by follow up hormone level assessment
  - Male sterilization (at least 6 months prior to screening). For female subjects on the study the vasectomized male partner should be the sole partner for that subject.
  - Combination of the following (a+b or a+c, or b+c):
    - a. Use of oral, injected or implanted hormonal methods of contraception or other forms of hormonal contraception that have comparable efficacy (failure rate <1%), for example hormone vaginal ring or transdermal hormone contraception
    - b. Placement of an intrauterine device (IUD) or intrauterine system (IUS)
    - c. Barrier methods of contraception: Condom or Occlusive cap (diaphragm or cervical/vault caps) with spermicidal foam/gel/film/cream/vaginal suppository

Post-menopausal women are allowed to participate in this study. Women are considered post-menopausal and not of child-bearing potential if they have had 12 months of natural (spontaneous) amenorrhea or 6 months of spontaneous amenorrhea with serum FSH >40 mIU/ml or 6 weeks postsurgical bilateral oophorectomy with or without hysterectomy.

Sexually active males unless they use a condom during intercourse while taking drug and for 3 months after the last dose of the study drug and should not father a child in this period. A condom is required to be used also by vasectomized men in order to prevent delivery of the drug via seminal fluid.

Patients with TIO who are currently taking BGJ398 or have been treated with BGJ398 in the past are eligible to participate in this study, provided that they discontinue BGJ398 for 2 weeks prior to the baseline visit.

*Abbreviated Title: BGJ398 in TIO*

*Version Date: 21MAY2019*

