### **2.2.2 Screening Visit**

Patients with a confirmed diagnosis of inoperable, metastatic, or non-localized TIO will be enrolled into this protocol by agreeing to and signing the informed consent and will undergo further eligibility screening (thoroughly evaluated based on the inclusion and exclusion criteria) at the NIH Clinical Center. This may be done as an inpatient or outpatient visit, at the discretion of the investigator and the subject. If eligible and the patient would like to begin drug immediately, the testing for the screening and baseline visits will be combined into a single inpatient visit. If not, the baseline visit and initiation of drug should occur within 6 weeks of the screening visit. Patients who have been previously treated with BGJ398 must be off BGJ398 for at least 2 weeks prior to the screening/baseline visit.

Procedures and tests during screening (if not combined with baseline visit) will include:

1. History
  - a. Detailed history of disease
  - b. Current medications including assessment of exclusionary medications/foods
2. Physical Exam
  - a. Height and weight measurement
  - b. Vital signs (pulse, blood pressure, temperature, and respiratory rate)
  - c. Physical examination
3. Blood tests
  - a. Blood chemistries: sodium, potassium, chloride, bicarbonate, creatinine, glucose, urea nitrogen, albumin, calcium, magnesium, phosphorous, alkaline phosphatase,

*Abbreviated Title: BGJ398 in TIO*

*Version Date: 21MAY2019*

- alanine aminotransferase (ALT), aspartate aminotransferase (AST), total bilirubin, direct bilirubin, LD, total protein, total CK, and uric acid
- b. Thyroid Stimulating Hormone (TSH) and Free Thyroxine (fT4)
- c. 25-OH vitamin D, 1,25 (OH)2-Vitamin D, intact PTH and FGF23 levels.
- d. Complete blood count (CBC): white blood cells (WBC), red blood cells (RBC), hemoglobin, hematocrit, mean corpuscular volume (MCV), red cell distribution width (RDW), and platelets.
- 4. Urine testing
  - a. Urine pregnancy test in females with childbearing potential.
  - b. Urinalysis: glucose, protein, urobilinogen, pH, hemoglobin, ketones, nitrite, leukocyte esterase, appearance, specific gravity, color, RBC, WBC, and squamous cells.
  - c. 24-hour urine for calcium, phosphorus, creatinine.
- 5. Imaging
  - a. FDG or Ga-DOTATATE PET/CT or Octreotide SPECT/CT if adequate study not done within the preceding 6 months.
- 6. Electrocardiogram to rule out exclusionary rhythm abnormalities.

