### 3.1.1 Drug-related adverse events (DRAE)

Drug-related adverse events (DRAE) will be defined as an AE or clinically significant abnormal laboratory value suspected to be related to therapy with BGJ398 (i.e., assessed as unrelated to disease progression, intercurrent illness, or concomitant medications), including those AEs and abnormal laboratory values that result in failure to meet the criteria for re-treatment or to begin a new cycle of therapy.

The criteria for defining DRAE are listed in (Table 3-1) using CTCAE v4.0.

Patients who experience a DRAE will have their therapy with BGJ398 interrupted and will be followed until the toxicity has resolved to CTCAE grade  $\leq 1$  or to the patient's baseline value. After recovery from the toxicity in question, if the investigator believes that it is in the patient's best interest to resume therapy with BGJ398, the patient may resume therapy at a lower dose level.

Prior to enrolling patients into a higher dose level, Grade  $\geq 2$  adverse events should be reviewed for all patients at the current dose level.

Table 3-1 Criteria for defining dose-modifications/interruptions for adverse events

TOXICITY	DRAE CRITERIA
Skipped/ delayed dose	The inability to administer BGJ398 on $\geq 75\%$ of scheduled treatment days during cycle 1 (i.e. $\geq 21$ days for a 28-days daily dosing schedule) due to unresolved adverse event of any grade and considered at least possibly, probably or definitely related to the study drug. Delay in 2 nd cycle administration due to failure of recovery from a possibly, probably or definitely related adverse event to grade $\leq 1$ or baseline by Day 43 (D28 of cycle 1 + 15 days), except for alopecia.
Blood/ bone marrow	Febrile neutropenia CTCAE Grade $\geq 3$ . Neutropenia CTCAE Grade $> 3$ for $> 7$ consecutive days. Thrombocytopenia  - CBC abnormalities CTCAE Grade 3 for $> 7$ consecutive days and/or with signs of clinically significant bleeding.  -CBC abnormalities CTCAE Grade 4. Anemia CTCAE Grade 4.
Renal/ genitourinary	Creatinine CTCAE Grade 1 for $> 7$ consecutive days and blood Pi $> 5.5$ mg/dL and/or blood tCa x Pi $> 55$ mg  /dL  and despite phosphorus lowering therapy for at least 14 days. Creatinine CTCAE Grade 2 for $> 7$ consecutive days. Creatinine CTCAE Grade $\geq 3$ .
Hepatic	Bilirubin CTCAE Grade 2 for $> 7$ consecutive days. Bilirubin CTCAE Grade $\geq 3$ . AST or ALT CTCAE Grade $\geq 3$ .

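### Exclusion 10 bars a patient only when ANC, platelets and hemoglobin are all low, so one or two severe cytopenias meet no numeric exclusion; its ANC line also gives two limits.

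*Combined protocol and SAP*

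**What the plan says.** Section 2.1.2 excludes a patient who meets any numbered item. Item 10 opens with "Insufficient bone marrow function defined as all of the following" and lists three limits. The first two lines are "ANC <1,500/mm 3 [1.0 x 10 9 /L] AND" and "Platelets < 75,000/mm 3 [75 x 10 9 /L] AND"; the third is hemoglobin under 10.0 g/dL. The conjunction is therefore stated twice, in the lead-in and in the connectors.

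Item 11, directly below, is built the other way: "Insufficient hepatic and renal function defined as one of the following", with OR between its lines.

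No other inclusion or exclusion criterion in Sections 2.1.1 and 2.1.2 sets a limit for a blood count. The only other hematologic entry wording is in the précis, where patients may be eligible if they "Have no significant ophthalmologic, gastrointestinal, renal, or hematologic disease". It carries no number.

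Section 2.2.2 has patients "thoroughly evaluated based on the inclusion and exclusion criteria" after consent, with a complete blood count among the tests. The Off-Study Criteria in Section 3.10 add screen failure and investigator judgment.

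**The concern.** A marrow-function exclusion normally protects a patient from starting a drug with any one count dangerously low. Read literally, item 10 does so only when all three cell lines have failed together. A patient with severe thrombocytopenia alone, or with severe neutropenia and anemia but adequate platelets, passes it. Item 9 expressly allows heparin, so the numeric criteria do not bar even a severely thrombocytopenic patient on heparin.

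What remains is the précis line and clinical judgment. Both can stop such a patient, but neither says at what count. Staff who apply the numbered list as written would find that this patient meets no blood-count exclusion.

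The ANC line has a separate fault: its two units give different limits. That has little effect under the present AND wording. It would matter as soon as the wording is corrected to OR, so the two faults belong in the same amendment.

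**Working it through.** This is a check of rule logic and units; no sample-size or interval formula applies.

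1. **Inputs (Section 2.1.2, item 10).** ANC below 1,500/mm3, with 1.0 x 10^9/L in the bracket; platelets below 75,000/mm3, with 75 x 10^9/L in the bracket; hemoglobin below 10.0 g/dL. Connector: AND.

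2. **Units.** Cells per mm3 x 10^6 = cells per L.
   - Platelets: 75,000 x 10^6 = 75 x 10^9/L. The bracket agrees.
   - ANC: 1,500 x 10^6 = 1.5 x 10^9/L. The bracket says 1.0 x 10^9/L, which is 1,000/mm3. It does not agree; the gap is 1,500 - 1,000 = 500/mm3.
   - Because the platelet line converts correctly, the ANC bracket looks like a conversion slip or a limit left over from another text. The documents do not say which figure is meant.

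3. **Logic.** Each count is low or not low, giving 2^3 = 8 patterns, of which 8 - 1 = 7 have at least one low count.

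| Rule | Patterns excluded | Patterns with a low count that pass |
|---|---|---|
| AND, as written | 1 (all three low) | 6 |
| OR | 7 | 0 |

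4. **Where the ANC discrepancy matters.** Take a patient with ANC of 1,000 to 1,499/mm3, who is low by one limit and not by the other. Platelets and hemoglobin give 2^2 = 4 patterns.
   - Under AND, the choice of ANC limit changes the decision only if both other counts are low: 1 of 4.
   - Under OR, it changes the decision only if neither other count is low: 1 of 4.
   - The number of patterns is the same, but the patients differ. Under OR the affected patient has a mildly low ANC and two adequate counts.

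5. **Is ANC measured?** The blood-count components listed in Sections 2.2.2 and 2.5 are white cells, red cells, hemoglobin, hematocrit, MCV, RDW and platelets. Neither list names a neutrophil count or differential. It may be reported routinely, but the text does not say so.

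Steps 3 and 4 count logical patterns. They are not probabilities and do not say how many patients would be affected.

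**The case against.** The best defense is that the rule is internally consistent: the lead-in and both connectors agree, so a permissive rule for a very rare disease could have been intended. Whether hemoglobin just under 10 g/dL should by itself cost a place in a 10-patient trial is a clinical question. That stands as a reason to have the clinicians confirm the change. It does not explain why three specific limits should bind only together, or how that fits the précis.

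Some stronger readings are tempting, but the documents do not support them:

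- **That item 10 contradicts item 11 and Table 3-1.** Item 11 concerns other organs, and its own transaminase line joins AST and ALT with a conjunction. Table 3-1 governs drug-related events during treatment, mostly at high grades (for example "CBC abnormalities CTCAE Grade 4. Anemia CTCAE Grade 4"), so it tolerates considerable single cytopenias. Both are contrasts. Only the précis is in real tension with item 10.
- **That a low count at entry simply becomes the level for restarting drug.** Section 3.1.1 does allow recovery to grade 1 or less "or to the patient's baseline value". But resumption also requires the investigator to judge it in the patient's best interest and is at a lower dose. Section 3.3 requires discontinuation if the same toxicity recurs at the same or worse severity.
- **That nothing can stop such a patient at screening.** The screen-failure rule says it includes meeting an exclusion criterion, so it is not limited to that. Hemoglobin and platelets are on the screening panel, and investigator judgment is available. What is missing is a threshold.
- **That many patients are at risk.** Section 11.1.2 reports anemia in 20.3% of 207 earlier patients, but this is any grade, regardless of cause, on treatment and in other tumors. No cytopenia is among the grade 3 or 4 events it names at 5% or more.

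**Conclusion.** The point holds as a fault in a written safety rule. As worded, item 10 excludes one of the seven patterns with a low count, and no other numeric entry criterion catches the remaining six. Entry of a patient with one or two severe cytopenias would be stopped only by an unquantified précis line or by judgment. A drafting error is the likeliest explanation, given the précis and the form of item 11, but that is inference about intent.

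The ANC line states two limits 500/mm3 apart. This matters little now and would matter under OR.

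The conclusion rests on the current text of Sections 2.1.1 and 2.1.2 and on applying item 10 literally. How often it would arise cannot be estimated, because the documents give no frequency of cytopenia in TIO. The primary endpoint, sample size and analysis are unaffected. The change should be made because it makes the rule safer at little cost.

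**What to change.** In one amendment:

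1. Reword item 10 so that any one of the three low counts excludes, with OR between the lines.
2. State one ANC limit in both units: either 1,500/mm3 with 1.5 x 10^9/L, or 1,000/mm3 with 1.0 x 10^9/L.
3. Have the clinicians confirm all three limits and the change to OR. If a more permissive rule was meant, state the floor for each count instead.
4. Name ANC (blood count with differential) among the screening and baseline tests in Sections 2.2.2 and 2.5. Under OR every patient needs it, whereas under AND it decides only when the other two counts are low.

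The cost is a short text change and a differential on a blood draw already scheduled, with no added visit. The downside is possibly one fewer eligible patient, for example one with hemoglobin just under 10 g/dL. Section 8.5 regards 10 as the most that can be enrolled, so that loss is real, but Table 8.4 already covers N=9. With five responders, the tabulated exact 95% interval widens from 81.3 - 18.7 = 62.6 points at N=10 to 86.3 - 21.1 = 65.2 points at N=9.

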### **3.3 DOSE MODIFICATIONS**

For patients who do not tolerate the protocol-specified dosing schedule, dose adjustments are permitted to allow the patient to continue the study treatment. The following guidelines need to be applied:

- These changes must be recorded in the patient's medical records and eCRF.
- All dose modifications should be based on the worst preceding toxicity.

*Abbreviated Title: BGJ398 in TIO*

*Version Date: 21MAY2019*

- Following resolution of toxicity to baseline or  $\leq$  grade 1, treatment is resumed at lower dose of study drug as per Table 3.3.1. If treatment is resumed at the lower dose of study drug, and the same toxicity recurs with the same or worse severity, the patient must discontinue study treatment.

Table 3.3.1 Dose reduction table:

BGJ398 dose level	BGJ398 dose
Starting level (0)	75 mg po once daily
Dose level-1	50 mg po once daily
Dose level-2	25 mg po once daily

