#### **Off-Study Criteria**

- Screen failure including meeting one of the exclusion criteria that cannot be resolved within 6 weeks of the screening visit.
- Subject noncompliance with study procedures.
- Completed study follow-up period.
- Participant requests to be withdrawn from study.
- Investigator judgment based on subject's best medical interest.

Abbreviated Title: BGJ398 in TIO

Version Date: 21MAY2019

- Death.

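### Exclusion 11 joins AST and ALT with 'and', so a patient with only one of the two above 2x ULN is not clearly excluded

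*Combined protocol and SAP*

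**What the plan says.** Section 2.1.2, criterion 11, opens with "Insufficient hepatic and renal function defined as one of the following" and lists three bullets:

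- total bilirubin above 1.5x ULN;
- "AST/SGOT and ALT/SGPT > 2x ULN OR";
- "Blood creatinine > 1.5xULN and/or calculated eGFR < 45 ml/min/1.73 m" squared.

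The rest of the protocol touches transaminases in four places.

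- **Table 3-1 (section 3.1.1).** The hepatic row counts "AST or ALT CTCAE Grade" 3 or higher as a drug-related adverse event, which interrupts treatment.
- **Recovery and restart (sections 3.1.1 and 3.3).** Recovery means Grade 1 or lower "or to the patient's baseline value". If the investigator thinks it in the patient's interest, "the patient may resume therapy at a lower dose level". Section 3.3 adds that if "the same toxicity recurs with the same or worse severity, the patient must discontinue study treatment".
- **Permanent withdrawal (section 3.10.1).** Transaminase abnormalities of Grade 4 or higher end treatment, with no condition that they be drug-related. A parenthesis names the enzymes, again joined by *and*.
- **Discretion (section 3.10).** The removal criteria and the Off-Study Criteria both include "Investigator judgment based on subject's best medical interest".

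**The concern.** The phrase *one of the following* chooses between bullets. It does not say how to combine the two enzymes inside the second bullet, where the connector is *and*. A site coordinator or monitor who applies the sentence as written would pass a patient with one clearly raised enzyme, provided the other is at or below 2x ULN.

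Three things are at stake.

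- **Safety at entry.** This is the stated hepatic threshold for a drug with a transaminase signal. Section 11.1.2 reports four dose-limiting toxicities in dose escalation. Two were Grade 3 AST/ALT elevations, one at 100 mg and one at 150 mg. The first dose is level 2 of this trial; the second is above its maximum of 125 mg. Drug-naive patients start at 75 mg and reach 100 mg only after the 8-week visit, if FGF23 is not suppressed. Previously treated patients start at their last dose.
- **Carry-forward.** Because baseline is an accepted recovery target, a raised entry value can become the level at which dosing may resume.
- **Consistent conduct.** The wording decides whether enrolling such a patient is a protocol deviation. Section 7.2.1 sends all deviations to the IRB, and section 8.1 drops patients with major deviations from the per-protocol population.

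**Working it through.** The plan gives no figure to reproduce here, so the check is logical.

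**Step 1. Write the criterion both ways.** Let A mean AST > 2x ULN, B mean ALT > 2x ULN, H mean bilirubin > 1.5x ULN, and R mean that the renal bullet is met.

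- Literal: exclude if H or (A and B) or R.
- Either-enzyme: exclude if H or A or B or R.

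**Step 2. Compare them with H and R false.**

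| AST > 2x | ALT > 2x | Literal | Either-enzyme |
|---|---|---|---|
| yes | yes | excluded | excluded |
| yes | no | not excluded | excluded |
| no | yes | not excluded | excluded |
| no | no | not excluded | not excluded |

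The readings differ only in the two discordant rows.

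**Step 3. Example.** Take ALT 4x ULN and AST 1.9x ULN. Since 4 > 2, B is true. Since 1.9 is not > 2, A is false. So (A and B) is false and the patient is not excluded literally, while (A or B) is true and the patient is excluded under the other reading.

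**Step 4. Look for another criterion that would catch this patient.** The remaining items in sections 2.1.1 and 2.1.2 set no limit on a single transaminase. Bilirubin is a separate test. The précis names ophthalmologic, gastrointestinal, renal and hematologic disease but not hepatic disease. Before dosing, only general investigator judgment remains.

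**Step 5. Which reading does the drafting support?**

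- *For either-enzyme:* Table 3-1 uses *or* for the same pair. The header of criterion 11 uses *and* as a plain list word for hepatic and renal function. Operators between bullets in criteria 10 and 11 are capitalised, while this *and* is lower case.
- *For the literal reading:* the renal bullet, also in lower case, uses *and/or* where either value is enough. The drafters had wording for either value and did not use it here.

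The balance favours either-enzyme as the intent, but the text does not say so.

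**Step 6. Bounds once the patient is on drug.** A drug-related Grade 3 or higher rise in either enzyme interrupts dosing. Restart is discretionary and at a lower dose. Recurrence at the same or worse severity ends treatment. Grade 4 or higher requires permanent withdrawal. The carry-forward route therefore operates only if a patient enters with one enzyme above Grade 1, has a drug-related event affecting that enzyme, recovers only to baseline, and is judged fit to resume.

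**The case against.** The strongest case against is that the literal reading is the less natural one. The *and* may simply name the two tests, as it most naturally does in the parenthesis of section 3.10.1. It would be uneven to read that parenthesis as a list and this bullet as a conjunction. This is a single-site study of about 10 patients, the team generally meets weekly to discuss those on treatment, and both enzymes are seen at screening. An investigator would be unlikely to dose a patient with a marked isolated rise.

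Much of this stands. The defect is an ambiguity with a probable benign intent, not a demonstrated gap in the sponsor's safety policy. What does not fall away is that an eligibility threshold should not depend on the reader's choice. The neighbouring *and/or* makes the conjunctive reading a reasonable one, and investigator judgment sets no level.

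Two stronger readings are tempting, and the documents support neither.

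- *A reader might infer that a patient could be enrolled and kept on treatment with one enzyme at any level.* The bullet itself has no cap on a single enzyme, but section 3.10.1 requires withdrawal at Grade 4 or higher regardless of cause, and the investigator may remove a patient sooner.
- *A reader might take the earlier dose-limiting toxicities as a measure of the risk.* They are on-treatment events in earlier studies, and section 11.1.2 reports AST and ALT together for both. They show that the liver signal is relevant. They do not show how often one enzyme alone exceeds 2x ULN at baseline in tumor-induced osteomalacia.

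**Conclusion.** The point holds as a wording defect in a safety criterion. Taken literally, exclusion 11 leaves patients with an isolated AST or ALT above 2x ULN eligible on hepatic grounds, and no other listed criterion closes the gap. The intended rule is probably either-enzyme.

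The size cannot be stated. The documents give no baseline transaminase data, and the number of patients affected may be zero. The consequence is confined to eligibility and safety: the primary endpoint, the planned 10 patients and the exact limits in Table 8.4 are untouched. The conclusion assumes that the parenthesis in section 3.10.1 means either enzyme, so that the Grade 4 rule does bound the exposure. If it were read conjunctively, that bound would be weaker.

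The change should be made: it is small, specific and improves safety at entry.

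**What to change.** In exclusion 11, change the second bullet to *AST/SGOT or ALT/SGPT > 2x ULN*. If the sponsor did intend a both-enzyme rule, the protocol should say so and justify it.

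As an optional alignment, write *(ALT or AST)* in the Grade 4 withdrawal rule of section 3.10.1.

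The cost is one word, or two with the optional change. AST and ALT are already in the screening and baseline chemistries (sections 2.2.2 and 2.5), so no test is added. The downside is an occasional extra screen failure, which is not trivial in a trial that expects to find only 10 eligible patients. If either-enzyme is already the intent, nobody the sponsor meant to enroll is lost.
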